1. GENERAL INFORMATION

1.1 Protocol Title: Epidermal Coverage of Traumatic Wound Injuries via Use of Autologous Skin Cell Harvesting Device in Combination with Widened Meshed Autograft Applied Over Bilayered Wound Matrix

2.1 Purpose

The purpose of this investigation is to evaluate the safety, tolerability, preliminary and long-term effectiveness of utilizing the ReCell Autologous Cell Harvesting Device (ReCell) combined with widened split-thickness skin graft (STSG) mesh onto the dermal regenerate INTEGRA™ Meshed Bilayer Wound Matrix (MBWM) for healing of full-thickness wounds.

2.2 Research Design

The proposed study is a prospective, single-center, randomized within-patient controlled feasibility study to evaluate the safety, tolerability, preliminary and long-term effectiveness of the ReCell Device for re-epithelialization (healing) of full-thickness wounds following previously successful treatment with INTEGRA™ MBWM.

2.3 Methodology /Technical Approach

In the proposed study, each patient will serve as his/her own control. Due to the nature of the study, only patients whose wounds have been previously successfully treated with INTEGRA™ MBWM as part of their standard of care will qualify for participation.

Therefore, as part of enrollment eligibility criteria for this study, the identified study wound will first be treated with INTEGRA™ MBWM. The wound will then be allowed to heal for approximately two to four weeks, at which time a viable granulation layer will have developed thus allowing for next stage STSG grafting. The timing of the STSG application will be determined by clinician judgment based on the state of the granulation process, which varies between patients, but typically takes 2 to 4 weeks.

Approximately two to four weeks after INTEGRA™ MBWM treatment, the studied wound will be divided into a ReCell-treated area (over 1:5 meshed STSG) and a control area treated with 1:1.5 meshed STSG (no ReCell). In all cases, the ReCell region may be up to 320cm² in size; the upper limit of application area for one ReCell kit, with a similarly sized control region. If the wound is larger than the combined ReCell and control regions (over 640cm²), the areas outside the study regions will be designated as non-study areas and treated according to standard of care. The same primary and secondary dressings will be used on ReCell-treated areas, control areas and donor sites. Once the study and control wounds are determined to have healed, standard local clinical practice will be followed.

Within-subject comparisons of the ReCell region and control region, in order to evaluate improvements associated with use of ReCell, a battery of measurements and evaluations will be made. These measurements are divided into three categories: safety and tolerability, preliminary effectiveness (acute healing process) and long-term effectiveness.

The safety of research participants is foremost. Therefore, efforts will be made to control risks to participants throughout the duration of their study participation. Wound healing time, donor site morbidity and histology will be assessed during an acute 6

week phase, with follow-up visits at Weeks 1, 2, 3, 4 and 6 post-treatment.

Subjects will continue in the study for long-term follow-up with clinic visits at Week 12 and 24 post-treatment. Healing of treated wound sites (A region and B region) and donor sites (STSG 1:5, STSG 1:1.5 and ReCell) will be assessed at each visit. Treated wounds will be considered healed when 95% or greater of the study area has re-epithelialized by Week 6 post-treatment. Donor sites will be considered healed when $\geq 95\%$ of the donor site has re-epithelialized by Week 4 post-treatment. Aesthetic and functional outcomes of the treated areas will be assessed and documented. Subject satisfaction will also be assessed and documented at these two time points.

3.OBJECTIVES AND SPECIFIC AIMS

The goal of the study described herein is to determine the safety, tolerability, preliminary and long-term effectiveness of the use of the Recell device over a widened STSG mesh. It is hypothesized the ReCell cell suspension, in combination with INTEGRA™ MBWM, will improve upon the current standard of care. The potential for ReCell's promotion of healing in the interstices of the STSG mesh may close gaps that are potential points of failure during subsequent rehabilitation and return to physical activity. Within the current study, each participant will serve as his/her own control, allowing for comparison of ReCell treated (experimental) and non-ReCell treated (control) regions of the grafted wound. The specific aims of this pilot clinical study are delineated below.

Specific Aim 1: Evaluate **safety and tolerability** of ReCell treatment of full-thickness wounds treated STSG over INTEGRA™ MBWM compared to control site. The safety and tolerability of ReCell treatment relative to standard of care (the control site) will be evaluated during the first 12 weeks after treatment, when the wound is most vulnerable for potential graft failure. Safety-related issues will continue to be monitored through 24 weeks after treatment.

Participants will be assessed for the following safety issues at each visit:

- Delayed healing/non-healing of wound and donor site
- Graft loss
- Heterotopic ossification
- Infection
- Scar contracture
- Durability (i.e. abrasions/injuries at graft site due to graft fragility)
- Allergic response to trypsin (the enzyme used in the ReCell process)
- Subject Complaint (i.e. pain and itching)
- Vital Signs
- Blood chemistries and hematology
- Other Treatment-related adverse events requiring surgical intervention prior to Week 12 post-treatment and all serious adverse event (SAE) occurrences throughout the study.

We predict non-inferiority in safety measures between ReCell-treated areas and control

areas of the wound.

Specific Aim 2: Evaluate the **preliminary effectiveness** of ReCell treatment of full-thickness wounds treated with STSG over INTEGRA™ MBWM compared to a control site. Preliminary effectiveness will be assessed during an acute healing phase (Week 1–6) and will focus on healing of both wound and donor sites. Evaluations to be performed include:

- Wound epithelialization
- Histology
- Patient pain rating

We predict that, at each time point, more ReCell-treated areas will be healed to an extent defined as non-inferior compared to the control areas of the wound.

Specific Aim 3: Evaluate the **long-term effectiveness** of ReCell treatment of full-thickness wounds treated with INTEGRA™ MBWM compared to a control site. Long-term effectiveness will be assessed at Weeks 12 and 24 post-ReCell treatment. Evaluations will focus on the integrity and durability of regenerated tissue as well as physical characteristics such as pliability and cosmesis. Patient satisfaction will also be evaluated. Evaluations to be performed include:

- Scar assessment scale using the Patient and Observer Scar Assessment Scale (POSAS) and Vancouver Scar Scale
- Functional outcome rating
- Patient satisfaction
- Histology
- Radiographic evaluation for assessment of heterotopic ossification

We predict that scar/functional outcomes and patient satisfaction metrics will be non-inferior for ReCell treated areas.

INTRODUCTION TO STUDY CONDUCT

This document is a protocol for a human research study. This study is to be conducted according to US and international standards of Good Clinical Practice (International Conference on Harmonization ICH E6), the Code of Federal Regulations Title 21 parts 803 and 812, and other applicable government regulations and Institutional research policies and procedures. No amendment to the protocol or deviation from the protocol will be implemented without the prior review and approval of the Institutional Review Board (IRB) except where it may be necessary to eliminate an immediate hazard to a research participant. In such a case, the deviation will be reported to the IRB as soon as possible.

4. BACKGROUND AND SIGNIFICANCE

4.1 Literature Review.

As survival rates of our war wounded continue to improve through significant advances

in our military's forward medical care, the number of complex soft tissue and orthopedic extremity injuries present difficult ongoing challenges. Extremity injuries secondary to war conflict, especially those caused by improvised explosive devices (IEDs), can result in massive soft tissue losses secondary to foreign body contamination, infection-related soft tissue necrosis, development of compartment syndromes, and secondary requirements for serial debridement and surgical procedures to aid in controlling the local wound environments. Often, these extremity injuries lead to significant utilization of health care resources not only within the post-trauma inpatient settings, but also through the course of the wounded service members extensive rehabilitation requirements.

In addition to the direct injury patterns and soft tissue losses experienced within certain wounded service members, donor site burdens for their reconstructions can also be rather significant. Many of the wounded service members who suffer from traumatic extremity injuries will require advanced reconstructions. These reconstructions typically involve complex soft tissue procedures often coupled with orthopedic surgeries to eventually cover vital structures and/or the soft tissue defects. Soft tissue injuries require various immediate as well as staged reconstructions including but not limited to need for eventual skin grafts, local or regional flaps, to advanced techniques such as microsurgical free tissue transfers.

Wounds that penetrate deep into the skin (full-thickness) remain a major clinical challenge to patients and reconstructive surgeons. Application of split or full-thickness skin grafts is associated with significant donor site morbidity (e.g., bleeding and scar formation) and often in the severely wounded patient, harvest sites are limited. For this reason, there has been much interest in the application of artificial substrates that can be used to enhance healing of the full-thickness wound. One such substrate is the INTEGRA™ MBWM (Integra Life Sciences Corporation, USA), a bilayer membrane designed to provide immediate coverage of full-thickness wounds. This wound care device is comprised of a porous matrix of cross-linked bovine tendon collagen and glycosaminoglycans and a semi-permeable polysiloxane (silicone layer). The semi-permeable silicone membrane controls water vapor loss, provides a flexible adherent covering for the wound surface and adds increased tear and suture retention strength to the device. The collagen-glycosaminoglycan biodegradable matrix provides a scaffold for dermal cellular invasion and capillary growth. During use, the INTEGRA™ MBWM is placed on a surgically debrided or excised wound, providing the needed framework for the blood vessels and dermal skin cells to remodel the damaged site. As skin cells migrate into the matrix, the collagen is slowly absorbed and replaced with collagen produced from the patient's own cells. In approximately 14 to 28 days, the scaffold is eventually remodeled as the patient's cells rebuild the damaged site. Once the dermal cells have integrated with the porous matrix, the silicone layer is removed and typically replaced with a thin meshed STSG. Application of the meshed STSG over INTEGRA™ MBWM is currently the standard care for patients with full-thickness wounds treated at Walter Reed National Military Medical Center (WRNMMC).

However, individuals who have sustained a traumatic injury, particularly wounded warriors, frequently possess limited donor site availability due to the nature and extent of associated injuries.

Therefore, harvest sites for the STSG are often limited. The ReCell Autologous Cell Harvesting Device system allows autologous transplant of the patient's own skin cells, including epidermal progenitor cells using a small thin biopsy site (typically no larger than 2 cm by 2 cm).

Our primary hypothesis is that when used in combination with a meshed STSG over INTEGRA™ MBWM, ReCell will produce non-inferior safety and performance using an expanded meshing ratio, thereby decreasing the required donor site and a secondary hypothesis of potential superiority to promote faster healing, minimization of mesh patterned scar and overall improved patient quality of life.

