5.7.2 Sample Size Estimation

No formal sample size estimation has been performed since this is a feasibility study. A sample size of 20 subjects was selected based upon the amount of subject exposure considered necessary in order for clinical assessments of safety, tolerability, preliminary and long-term effectiveness of the ReCell device when used for healing of full-thickness wounds treated with 1:5 meshed STSG and INTEGRA MBWM. This study does not evaluate formal hypotheses and is not prospectively powered to detect potentially clinically significant improvements in study endpoints. The results of this feasibility study may be analyzed to refine the study design for a pivotal trial.

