5.7.3 Data and Statistical Analysis Plan

Due to the feasibility nature of this clinical trial, no formal statistical analysis nor interim analysis will be performed. Data collected in this study will be documented using summary tables. Quantitative variables will be summarized using descriptive statistics, including mean (and/or median), standard deviation (SD), and when appropriate minimum and maximum values. Categorical variables will be summarized by frequencies and percentages. Where appropriate, 95% confidence intervals either around the sample means or mean differences will be furnished. All data collected will be presented in subject data listings.

Power Analysis

Post hoc power analysis was conducted using G*Power 3.1 (Faul, Lang, & Buchner, 2007) for this 2 x 7 mixed design (i.e., two treatment groups x 7 waves of measurements). Given the constraints on sample size ($n = 20$), a power analysis was conducted with the intent to detect the obtained power ($1 - \beta$) given: (1) level of significance (set at $\alpha = .05$), effect size (standardized F statistic varied at .15, .2, and .25) and (3) rate of autocorrelation (average correlations of repeated measures varied at .3, .5, and .7). Even though ascertaining what constitutes a small/medium/large effect size is, in part, context and discipline-dependent, using Cohen's (2008) taxonomy of small ($F = .10$) and medium ($F = .25$) we see below that sufficient power (.80) to obtain significance for the 2 x 7 first order interaction will be obtained for a medium effect size when the autocorrelation is .5 or higher and for a slightly smaller effect size ($F = .2$) when autocorrelation approximates .7. However if the effect size approximates .15 sufficient

power will not be obtained, regardless of magnitude of autocorrelation.

AutoCorr	Effect Size	Power
0.3	0.25	0.729
0.5	0.25	0.881
0.7	0.25	0.989
0.3	0.2	0.503
0.5	0.2	0.672
0.7	0.2	0.904
0.3	0.15	0.286
0.5	0.15	0.399
0.7	0.15	0.639

Cohen (1988). *Statistical power analysis for the behavioral sciences*. (2nd Ed.). Hillsdale, NJ: Lawrence Erlbaum.

Proposed Analysis

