For this 2 x 7 mixed design (i.e., two treatment groups x 7 waves of measurements) with a continuous level outcome, a two-way (completely within) repeated measures ANOVA will be performed with the overarching objective being the test of significance for the two-way treatment x time interaction (using $\alpha = .05$). If the two-way interaction is significant, simple effects analysis will be performed so as to assess at which time point significant differences for the treatment variable are obtained. Moreover, if the first order interaction is significant, trend analysis will be conducted in an effort to uncover any nonlinear patterns across time (up to polynomial $t - 1$, where $t = \text{time}$). Graphic displays will be provided so as to illuminate the nature of the findings and the between treatment trajectories.

All assumptions will be examined, including sphericity and homogeneity of variance/covariance matrices and any data anomalies (e.g., outliers) will be examined and treated accordingly. It should be kept in mind that given the small sample size ($n = 20$), there may still be substantive effects despite non-significant results, hence univariate and multivariate effect sizes will be reviewed (e.g., partial η^2).

There are many techniques beyond a mixed ANOVA approach that can more dynamically model the longitudinal nature of this design, such as multilevel modeling, generalized estimating equations, and/or latent growth curve modeling. However, those techniques will need to be deferred until a larger sample size is obtained. All analysis will be conducted using SPSS 21.0 or Stata 11.0.

Analysis Sets of ReCell Device Treatment vs. Control Comparison:

Safety Analysis Set:

The safety analysis population will include all enrolled subjects. Data will be analyzed based on treatment received. The number and percentage of subject who discontinued the study due to adverse event will be provided. Also, descriptive statistics, as

appropriate, will be provided for the following, by treatment:

- Delayed healing/non-healing of wound and donor site
- Graft loss
- Heterotopic ossification
- Infection
- Scar contracture
- Durability (i.e. abrasions/injuries at graft site due to graft fragility)
- Allergic response to trypsin
- Subject Complaint (pain and itching)
- Vital Signs
- Blood chemistries and hematology

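### The primary hypothesis and all three aims claim non-inferiority, but the available text gives no margin or interval rule, and the only planned test (treatment by time) cannot address the claim

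*Combined protocol and SAP*

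**What the plan says.** **The claim.** The primary hypothesis, at the end of Section 4.1, is that "ReCell will produce non-inferior safety and performance using an expanded meshing ratio"; superiority is secondary. Section 3 repeats the form for each aim:
- Aim 1: "We predict non-inferiority in safety measures between ReCell-treated areas and control" areas.
- Aim 2: "more ReCell-treated areas will be healed to an extent defined as non-inferior compared to the control areas of the wound".
- Aim 3: "We predict that scar/functional outcomes and patient satisfaction metrics will be non-inferior for ReCell treated areas".

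Aim 2 refers to a definition of non-inferior, but none is given in the available text.

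**The analysis.** Section 5.7.3 plans a two-way repeated-measures ANOVA on a continuous outcome that it does not name, with the "overarching objective being the test of significance for the two-way treatment x time interaction" at alpha .05. Simple effects by visit follow only if that interaction is significant. The power table in the same section is for the interaction. The safety endpoints receive descriptive statistics by treatment. Confidence intervals at 95% are offered for means or mean differences where appropriate.

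**The disclaimers.** Section 5.7.2 says "This study does not evaluate formal hypotheses and is not prospectively powered", and Section 5.7.3 opens by saying that "no formal statistical analysis nor interim analysis will be performed".

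**The concern.** A non-inferiority claim needs a margin and a rule that compares a confidence limit with it. The plan has the claim without either, and its one inferential procedure answers a different question. The disclaimers do not settle the matter, because the same section goes on to set an alpha level, a power table and follow-up tests.

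Section 5.7.2 says the results may be used to refine a pivotal trial. A statement that ReCell was non-inferior on graft loss or infection, with no agreed meaning, could then be carried forward as if the study had established it.

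**Working it through.** **1. What the printed power table measures.** The inputs are in Section 5.7.3: N = 20, m = 7 visits, alpha .05, f = .15 to .25, average correlation rho = .3 to .7. For the interaction, the noncentrality is lambda = f² × N × m / (1 − rho), with 6 and 108 degrees of freedom.

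Example: f = .25, rho = .5 gives lambda = .0625 × 20 × 7 / .5 = 17.5. The critical F is 2.184 and the power .881, as printed. All nine printed values (.286 to .989) reproduce within .001. The table is therefore power to detect a difference in time course. No entry is power for non-inferiority.

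**2. Whether the interaction can address the hypothesis.** Let d(t) be the mean ReCell-minus-control difference at visit t. The interaction tests whether d(t) − mean(d) is zero at every visit. If ReCell is worse by the same amount d at each visit, d(t) − mean(d) = d − d = 0 whatever the size of d. The stated main test is then at its null.

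**3. Whether it fits the endpoints.** The test needs a continuous outcome at seven visits.
- Graft loss, infection, contracture and delayed healing (primary, Section 5.7.1) are naturally yes/no.
- The Vancouver Scar Scale, functional rating and satisfaction are taken only at Weeks 12 and 24.
- The patient part of the POSAS is taken at all seven post-treatment visits, so it could fit.

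**4. What 20 pairs could show on a yes/no outcome.** The plan gives no margin and no rate per region, so these inputs are assumed: true event rates equal at 5% or 10% (Section 6.2 puts total graft loss at 5% to under 10%, in a list of risks to the subject, not per region); regions independent within subject; paired score (Tango) test, one-sided .025; all outcomes enumerated.

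Let b and c be the numbers of subjects with a ReCell-only and a control-only event. For margin M, z = (b − c − nM) / √[n(2q + M(1 − M))], where q is the estimated control-only probability under the margin. Non-inferiority requires z ≤ −1.96.

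| Event rate | Discordant pairs expected | 10 points | 15 points | 20 points |
|---|---|---|---|---|
| 5% | 2 × .05 × .95 = 9.5% | .104 | .267 | .622 |
| 10% | 2 × .10 × .90 = 18% | .126 | .227 | .487 |
| 5%, discordance halved | 4.75% | .052 | .244 | .731 |

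With b = c = 0, q is 0 and the upper 95% limit solves nM/(1 − M) = 1.96², so M = 3.84 / (20 + 3.84) = .161. One discordant pair each way gives .199. At margins of 10 or 15 points, even complete agreement between the regions would not be enough.

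**5. What 20 pairs could show on a scale.** For a paired t test, one-sided .025, no true difference, and a margin of k SDs of the within-subject difference, power is P(T > 2.093), where T is noncentral t with 19 degrees of freedom and noncentrality k√20.

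| k | 0.2 | 0.3 | 0.4 | 0.5 | 0.66 | 0.8 |
|---|---|---|---|---|---|---|
| Power | 13% | 25% | 40% | 56% | 80% | 92% |

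**The case against.** Three stronger readings are tempting, and the documents do not support them.

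- **That a non-significant result will be taken as non-inferiority.** No passage says so. Section 5.7.3 warns that real effects may exist despite non-significance and points to effect sizes. That caution stands, but effect sizes such as partial eta-squared are not a non-inferiority criterion.
- **That a higher rate of graft loss or infection would pass the plan's test.** The plan applies no test to these outcomes; they are summarised and listed. The gap is that no paired comparison is specified for them.
- **That 20 subjects can never show non-inferiority.** That depends on the margin. About 0.66 SD of the paired difference gives 80% power. Both regions lie in one wound, so outcomes are probably positively correlated. At a 5% rate, a 20-point margin gives 73% with discordance halved and 83% with it quartered. A normal approximation gives 81% at 10% discordance (Φ[.20 × √(20/.10) − 1.96]), but the enumeration gives 62% at 9.5%, so it is optimistic here.

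It is also fair to say that this is a feasibility study, that the aims predict rather than set a success criterion, and that intervals for mean differences are already offered. This lowers the severity. Appendix H, listed as including a statistical management plan, is not in the available text and could define a margin. If so, Section 5.7.3 should state it.

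**Conclusion.** The point holds as a mismatch between claim and analysis. The primary hypothesis and all three aims assert non-inferiority. The available text gives no margin or interval rule, and the one planned test and its power table cannot bear on the claim. The statements about formal hypotheses and formal analysis also contradict the planned alpha .05 test.

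Under the independent-region assumptions above, power for non-inferiority on a yes/no outcome is roughly 10-13%, 23-27% and 49-62% at margins of 10, 15 and 20 points. Only wide margins approach 80%. The margins, the rates per region and the within-subject correlation are all illustrative; the textual mismatch depends on none of them. This should be fixed, but it is a reconciliation of wording and reporting and not a flaw in the conduct of the study.

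**What to change.** 1. In Sections 3 and 4.1, replace the non-inferiority hypothesis and predictions with estimation: the within-subject ReCell-minus-control difference will be reported with a two-sided 95% interval, and no conclusion of non-inferiority or equivalence will be drawn from this study.
2. In Section 5.7.3, report a paired risk difference with 95% interval for each region-level yes/no outcome. For scales, make the paired mean difference with 95% interval standard instead of leaving it to be given where appropriate.
3. Label the ANOVA and its power table exploratory, and name the outcome to which the ANOVA applies.
4. Make Sections 5.7.2 and 5.7.3 agree that no confirmatory test is performed.

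The cost is text only: no new data, visits or subjects. The downside is that the conclusion the study can state becomes less favourable. If the sponsor prefers to keep a non-inferiority claim, the endpoint, the margin and the interval rule must be fixed before the data are seen, and the calculations above suggest that 20 pairs would serve only a wide margin.
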